#### **Lever Out/Push Out Testing**

Testing was performed on the worst case component of each material insert to compare the dislocation resistance of the inserts by characterizing their lever out and pull out strengths. The following smallest and thinnest available components were identified as the worst case from each material: X3® part number 1236-2-846 (28 mm ID/ 46 mm OD) & Duration® part number 1235-2-246 (22.2 mm ID/ 46 mm OD). Seventeen test samples were used for each material in both lever-out and pull-out tests. The results of the testing showed that the lever-out and pull-out resistance strengths of the worst case X3® Acetabular Insert were not less than the worst case Duration® Acetabular Inserts, meeting the test acceptance criteria. Ease of use with instrumentation was also identified to be similar between the X3® and Duration® Acetabular Inserts. Refer to test reports TR09-1014, entitled Comparative Lever-Out & Axial Pull-Out Testing of Restoration® ADM X3®, for detailed methods and results.

#### **Contact Stress Analysis**

The contact stress within the subject Restoration® ADM X3® Acetabular Inserts are comparable to those of its predicate Trident® X3® Acetabular Inserts.

#### **Materials**

The subject X3® and predicate Duration® Acetabular Inserts are manufactured from UHMWPE meeting American Society for Testing Materials (ASTM) Standard F648. The predicate Duration® Acetabular Insert device is fabricated from GUR 1050 UHMWPE. The X3® Acetabular Insert is manufactured from compression molded GUR 1020 polyethylene. Manufacturing changes have been made to the processing of the raw material to provide a sequentially crosslinked and annealed polyethylene material for use in the manufacturing of the inserts. See Table 1 for a summary of Duration® and X3® properties. Based on the comparative results below, the 1020 GUR is acceptable for use in combination with the Restoration® ADM Acetabular Shell for THA.

Table 1. Subject Polyethylene Properties

Property	Duration Polyethylene 1050 GUR Mean (Std. Dev.)	X3 ® Polyethylene 1020 GUR Mean (Std. Dev.)
UTS (MPa)	51.1 (3.3)	56.7 (2.1)
Yield Strength (MPa)	24.3 (0.5)	23.5 (0.3)
% Elongation	404 (16)	267 (7)
Density (kg/m³)	929.2 (0.0)	939.2 (0.1)
% Crystallinity	56.7	61.7 (0.6)

The results of the bench top testing conducted for the new Restoration® ADM X3® Acetabular Inserts identified acceptance criteria was met.

The following bench tests were conducted with the Accolade® II Hip Stem:

- 127° Accolade® II Size 3 Neck Verification Testing (RD-10-095)
- 127° Accolade® II Size 0 Distal Body Verification Testing (RD-10-096)
- 127° Accolade® II Size 2 Neck Verification Testing (RD-11-022)

The results of the bench top testing conducted for the new Accolade® II Hip Stem identified acceptance criteria were met.

Copies of all test reports are available at Stryker Orthopaedics.

#### 1.4 Clinical Data to Date

This study is the first Stryker sponsored multi-center prospective data collection on the Restoration® ADM X3® Acetabular System and the Accolade® II Hip Stem.

# 2 Study Objectives

# 2.1 Efficacy

#### 2.1.1 Primary

The primary objective of this study is to evaluate the success rate of cementless primary total hip replacement (THR) with the Restoration® ADM X3® Acetabular System as compared to the published results of primary THR systems. Success will be defined as absence of femoral head dislocation at 10 years postoperative. It is expected that the survivorship of the Restoration® ADM X3® Acetabular System group will be non-inferior to the survivorship reported in the literature for other primary THR systems.

# 2.1.2 Secondary

The secondary objectives of this study will be to evaluate all-cause revision and removal rates with the Restoration® ADM X3® Acetabular System and compare with those reported for other primary hip systems in the literature.

Additionaly, psoas impingement and associated groin pain, function and health-related QOL between the Restoration® ADM X3® Acetabular System and those reported in the literature for other primary hip systems and similar dual mobility cups on the market will be compared at postoperative time points.

Lastly, radiographic stability and complications between those implanted with the Restoration® ADM X3® Acetabular System and other primary hip systems in the literature will be reviewed.

#### **Clinical Outcomes:**

Clinical outcomes will be evaluated with the total HHS, including pain, motion and function, preoperatively and at the 6-week, 1, 2, 3, 4 and 5-year visits. Additional

HHS data will be obtained at the 7-year and 10-year time points at investigational sites that choose to bring their subjects in for these optional visits.

#### **Patient Outcomes:**

Pain, function and health related QOL will be compared between the Restoration® ADM X3® Acetabular System and reports in the literature for other primary THR systems and similar dual mobility cups on the market. The SF-12 is a 12 item patient self-assessment evaluating health and general well being. The LEAS is a tool that has been developed and validated to evaluate the level of patient activity. The EQ-5D is a standardized instrument for use as a measure of health outcome. These tools will be used to assess patient health-related QOL and will be collected preoperatively at the 6-week, 1, 2, 3, 4, and 5-year visits.

A Follow-Up Questionnaire will be administered annually in postoperative years 6-10 to assess patient satisfaction and pain, and to capture AEs. This questionnaire will provide the survivorship information necessary to evaluate the primary objective of the study. Patient outcomes data will also be obtained at the 7-year and 10-year time points at investigational sites that choose to bring their subjects back in for these optional visits, in addition to the required Follow-Up Questionnaire described.

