#### Secondary:

- The Kaplan-Meier survival curve of revision/removal for the Restoration® ADM X3® Acetabular System (acetabular shell and insert) will be displayed.
- A paired t-test will evaluate the changes in clinical and patient outcomes (HHS, SF-12, EQ-5D, and LEAS), preoperative to 5 years postoperative within the Restoration® ADM X3® Acetabular System (acetabular shell and insert) group, when data is available. In addition, the mean scores (HHS, SF-12, EQ-5D, and LEAS) over time will be tabulated, with standard deviation and 95% confidence intervals presented, if applicable.
- The AE rates and radiographic data will be listed and tabulated at 10 years postoperative for the Restoration®
   ADM X3® Acetabular System group, with 95% confidence intervals presented, if applicable.

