# 2.2 Safety

All operative site events as well as all serious adverse events (SAEs), excluding elective procedures, will be collected and compared to published data. It is expected that the AE rates reported for the Restoration® ADM X3® Acetabular System will be comparable to those reported in the literature for other primary THR systems and similar dual mobility cups on the market. Details regarding AE definitions, recording and reporting are in Section 8 of this protocol, Adverse Events.

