### 7.4 Annual Follow-up Visits

Clinical data will be collected via office visit by the investigator at the following annual postoperative intervals: 1-year, 2-year, 3-year, 4-year and 5-year. Tools for postoperative evaluation will be the HHS, AP pelvis, AP femur and lateral radiographs. Radiographs will also be obtained at 1 year and then annually to 5 years postoperatively.

Patient outcomes data will also be collected with the required SF-12, LEAS, and EQ-5D patient questionnaires at each annual visit at the 1-year through 5-year follow-up visits.

All clinical data, radiographs, and patient outcomes data must be collected within  $\pm$  2 months of the 1-year and 2-year anniversary dates. For remaining annual time points, the window expands to  $\pm$  3 months of the 3-year anniversary date and  $\pm$  4 months of the 4-year through 10-year anniversary dates.

The initial phase of the study will continue for 5 years after surgery and include collection of the previously described radiographs, HHS, SF-12, LEAS and EQ-5D patient questionnaires. In the second phase of the study, all subjects will complete a brief Follow-up Questionnaire annually at the 6-year, 7-year, 8-year, 9-year and 10-year follow-up intervals. This form may be completed by the SC during a subject telephone interview, or by the subject either at home or during a clinic visit. The questionnaire will be used to obtain the following information, at a minimum:

- Subject satisfaction with the hip replacement
- Presence of any pain in the study hip
- Any surgeries performed on the study hip
- Any dislocations in the study hip

The questionnaire will also provide information on any revisions and enable calculation of the Kaplan-Meier Survival Curve necessary to meet the primary endpoint of the study.

Additionally, at investigational sites that choose to continue collecting clinical and radiographic data during the second phase of the study, subjects will be evaluated again at 7 and 10 years after surgery.

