# **8 Adverse Events**

### 8.1 Reporting of Adverse Events

The AE reporting requirements for this study are as follows:

- All AEs that meet the definition of serious, excluding elective procedures
- All AEs related to the operative site, regardless of seriousness

Elective procedures meeting the definition of an SAE do not need to be reported as AEs according to this study protocol. Examples of such elective procedures include, but **are not limited to**, the following commonly seen events:

- Contralateral THR
- Total Knee Replacement
- Rotator Cuff Surgery
- Cataract Surgery

Such events will not be captured on the AE electronic Case Report Form (eCRF) but rather will be captured on the Postoperative Functional Evaluation at the 6-week, 1-year, 2-year, 3-year, 4-year and 5-year time points. Additional events of this nature will be captured on the 7-year and 10-year functional evaluations if the investigator chooses to bring subjects in for these optional visits. On these functional evaluations, investigators and SCs will be prompted to question subjects as to whether they have seen a doctor for any reason, been hospitalized for any reason or have a current impediment to their function.

Additionally, SCs will be responsible for following up with the subjects regarding any questionable responses received on the Follow-up Questionnaire administered in postoperative years 6 through 10. If it is determined upon this further investigation that a protocol-defined AE has

Restoration® ADM X3® Study with Long Te Stryker Orthopaedics Clinical Study Protoc Version 3.0	erm Data Collection for the Accolade ® II Hip Stem col	Page 30
occurred, the SC will be responsib	le for completing an AE eCRF, submitting the e	event to Stryker
and reporting to the IRB, as require	ed.	

The following decision tree facilitates identification of AEs for which reporting is required under this study protocol:

Start Site becomes aware of Adverse Event Is the event related to the Does the AE meet the Do NOT report to No-No→ operative site? criteria for Seriousness? Stryker Yes Yes Report AE to Stryker via AE Is the event an Yes-Form elective surgery? No Report AE to Stryker via AE Form End

Figure 4. Adverse Event Decision Tree

CONFIDENTIAL

This material is the property of Stryker Orthopaedics. Do not disclose or use except as authorized in writing by Stryker.

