## Restoration®ADM X3®Acetabular System POST-OP FUNCTIONAL EVALUATION

| IV. EVENTS                                                               |                                                                           |                          |        |                                         |  |  |  |  |  |  |
|--------------------------------------------------------------------------|---------------------------------------------------------------------------|--------------------------|--------|-----------------------------------------|--|--|--|--|--|--|
| K. Have there been any protocol                                   | defined Adverse Events sin                                                | nce the last visit?      | Yes*   | ○ No
ete an AE form for each. |  |  |  |  |  |  |
| USE THIS SECTION TO REPORT M                                             | EDICAL EVENTS OTHER THA                                            | N PROTOCOL DEFINE        |        |                                         |  |  |  |  |  |  |
| L. Has the subject seen a doctor                                         | Has the subject seen a doctor for any medical event since the last visit? |                          |        |                                         |  |  |  |  |  |  |
| *If Yes, specify:                                                        |                                                                           |                          |        |                                         |  |  |  |  |  |  |
|                                                                          |                                                                           |                          |        |                                         |  |  |  |  |  |  |
| M. Has the subject been hospita  *If Yes, specify (check all that apply) | lized for any elective surge                                              | ry since the last visit? | ○ Yes* | ○ No                                    |  |  |  |  |  |  |
| Contralateral Hip                                                        | Contralateral Knee                                                        | Ipsilateral Knee         | [      | Contralateral Shoulder                  |  |  |  |  |  |  |

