|                                                                                                                   |                                         |             |            |  |  |  |
|                                                                                                                   |                                         |             |            |  |  |  |
| 2. Are you satisfied with the results of your study h                                                             | in ranlacament?                         | O VEC       | ONO        |  |  |  |
| Subject comment:                                                                                                  | ip replacement.                         | YES         | ○ NO       |  |  |  |
|                                                                                                                   |                                         |             |            |  |  |  |
|                                                                                                                   |                                         |             |            |  |  |  |
| Coordinator comment:                                                                                              |                                         |             |            |  |  |  |
|                                                                                                                   |                                         |             |            |  |  |  |
|                                                                                                                   |                                         |             |            |  |  |  |
|                                                                                                                   |                                         |             |            |  |  |  |
| 3. Have you had any surgery on your study hip since                                                               | your last study required visit/contact? | YES         | ○ NO       |  |  |  |
| Subject comment:                                                                                                  |                                         |             |            |  |  |  |

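### After year 5 the only mandatory form has no general adverse-event question, so 10-year rates of non-hip SAEs and some operative-site events are likely to be understated by an unknown, site-dependent amount

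*Combined protocol and SAP*

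**What the plan says.** **The safety objective.** Section 2.2 states: "All operative site events as well as all serious adverse events (SAEs), excluding elective procedures, will be collected and compared to published data". The synopsis, under the secondary statistical methods, adds: "The AE rates and radiographic data will be listed and tabulated at 10 years postoperative". Section 8.1 (Adverse Event Reporting Period) runs reporting from consent to study completion and obliges the investigator to ask specifically about AEs at each contact. Section 8.4 extends recording to events that fall between visits.

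**Years 6 to 10.** The required contact is the annual Follow-up Questionnaire. Section 2.1.2 gives its purpose: "A Follow-Up Questionnaire will be administered annually in postoperative years 6-10 to assess patient satisfaction and pain, and to capture AEs". Section 7.4 allows completion in a telephone interview with the coordinator or "by the subject either at home or during a clinic visit", and the form in Appendix F also offers a mail option. Its items are present hip pain, satisfaction, surgery (item 3 begins "Have you had any surgery on your study hip since") and dislocation. Section 7.4 lists the same four topics as a minimum.

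**Handling of answers.** Section 8.1 says "SCs will be responsible for following up with the subjects regarding any questionable responses received on the Follow-up Questionnaire". The form itself tells the coordinator to review every response for a possible AE.

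**To year 5.** The Post-op Functional Evaluation carries item K, which asks directly whether any protocol-defined AE has occurred since the last visit. It is mandatory to year 5. At years 7 and 10 it is used only at sites that choose the optional visits.

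**The concern.** The questionnaire is given the job of capturing AEs, but none of its items asks about hospital admission, illness or infection. The description of the form under the Evaluation Schedule mentions dislocation, satisfaction, pain and revision or removal, and not AEs in general. The reporting duty thus runs to year 10 while the mandatory prompt that serves it stops at year 5.

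Take a subject admitted in year 7 with a stroke and a well-functioning hip. The four truthful answers are no pain, satisfied, no surgery and no dislocation. If the form is posted back, nothing on it tells the site that a reportable event occurred.

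At stake is the 10-year AE comparison with published data. Section 2.2 expects the rates to be comparable to the literature, and missed events push the observed rates down, which favours the study device. Capture would also vary between sites and completion modes within a single pooled rate.

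**Working it through.** The plan gives no SAE rate or expected count, so there is no figure to reproduce. The main check sets the two instruments in Appendix F against the duty in section 8.1.

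1. *Direct AE prompt.* Post-op Functional Evaluation: item K. Follow-up Questionnaire: none.
2. *Wider medical prompts.* On the Post-op Functional Evaluation, item L asks "Has the subject seen a doctor for any medical event since the last visit", item M asks about hospitalisation for elective surgery only, and item N about current function. This block is reserved for events other than protocol-defined AEs, so item K is the prompt that matters. The general hospitalisation question described in section 8.1 is not printed as such on the form. Follow-up Questionnaire: none.
3. *Look-back.* On the questionnaire only items 3 and 4 (surgery, dislocation) refer back to the last contact. Item 1 asks about pain now. A hip infection or other operative-site event that settled without surgery can go unreported, although section 8.1 requires operative-site AEs whatever their seriousness.
4. *Mode.* A telephone or clinic contact can carry the specific questioning that section 8.1 requires. A form completed at home and mailed has no such step. The documents do not say how many forms will come back that way.
5. *Site.* Where the optional visits are held, item K asks about the time since the last visit, so prompted coverage can extend to 10 years. Elsewhere it covers 5 of 10 years.
6. *Deaths.* The Study Termination form requires an AE form, so fatal events have their own route.

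**Range of effect.** Let *s* be the share of year 6-10 SAEs still captured (0 to 1, unknown). Effective SAE follow-up is 5 + 5*s* years: 5.0 at *s* = 0, 6.25 at 0.25, 7.5 at 0.5, 8.75 at 0.75 and 10 at 1.

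For illustration only, assume a constant SAE rate *h* per subject-year and no loss to follow-up. The share of subjects with at least one captured SAE by year 10 is 1 - exp(-*h*(5 + 5*s*)). The values of *h* are assumptions; none is in the documents.

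| Assumed *h* | *s* = 1 (true) | *s* = 0.5 | *s* = 0 |
|---|---|---|---|
| 2% per year | 18.1% | 13.9% | 9.5% |
| 5% per year | 39.3% | 31.3% | 22.1% |
| 8% per year | 55.1% | 45.1% | 33.0% |

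For example, at 5%: 1 - exp(-0.5) = 0.393 against 1 - exp(-0.25) = 0.221, a relative shortfall of (0.393 - 0.221)/0.393 = 43.8%. Over the three rates the shortfall is 40-48% at *s* = 0, 18-23% at *s* = 0.5 and zero at *s* = 1. The direction is the same for any *s* below 1.

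**The case against.** The strongest reply is that the protocol does not end SAE collection at year 5. Section 8.1 requires specific questioning at each contact through study completion, section 8.4 covers events between visits, and deaths need an AE form. Questionnaires done by telephone or in clinic are contacts at which that duty applies in full. Section 7.4 sets only a minimum content, and every item on the form has free-text space for the subject and the coordinator.

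A reader might infer that the 10-year SAE rates would in practice reflect about 5 years of collection and fall short by 40-48%. The documents do not support that. It requires no capture at all after year 5, ignores the routes above and the optional visits, and rests on assumed rates. Nor is the formula the planned statistic: section 9.2.2 plans counts and percentages of cases or subjects, and section 9.4.2 allows for 20% loss to follow-up.

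A reader might also infer that coordinators act on nothing but questionable answers. Section 8.1 does not say so, and the form asks for review of all responses.

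The AE analysis is descriptive, with no test or success criterion, and a short questionnaire in the second phase is a reasonable way to limit burden.

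These points rule out the extreme reading and limit the consequence. They do not close the gap. Reviewing four unremarkable answers on a mailed form cannot reveal a stroke, and a duty to record an event does not tell the site that it happened.

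**Conclusion.** The point holds as a likely, unquantified under-ascertainment. After year 5, capture of non-fatal, non-hip SAEs, and of operative-site events that resolved without surgery, is likely to be incomplete and to differ by site and by how the form is completed. The pooled 10-year rates set against the literature would then be too low.

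The documents fix only a range: effective SAE follow-up between 5 and 10 years, depending on *s*. The 40-48% figure is the zero-capture bound under assumed rates of 2-8% per year and should not be cited as an estimate.

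The primary endpoint is not touched, because dislocation is asked about every year to year 10, as is study-hip surgery. The conclusion assumes that some questionnaires are self-completed without an interview, as section 7.4 permits, and that not every site holds the optional visits. It is worth acting on because a stated safety objective is affected and the remedy is cheap.

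**What to change.** Add two separate yes/no parts to the Follow-up Questionnaire in Appendix F and to the minimum list in section 7.4. Use them in every completion mode, to do the work that item K does on the visit form:

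- (a) *Since your last study contact, have you been admitted to hospital or had a serious illness for any reason?*
- (b) *Since your last study contact, have you had any infection, fracture or other problem with your study hip?*

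Any yes triggers the section 8.1 AE check. Keeping the parts separate stops the hip wording from narrowing the general question. Copying items L and M would not serve, since they concern events outside the protocol-defined AEs.

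In section 9.2.2 and the synopsis, tabulate non-hip SAE rates separately for years 0-5 and 6-10, and keep every reported event in the tables. For year 6-10 data collected without the new question, state the ascertainment limit beside the rates.

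The cost is a minor amendment, an eCRF update and some coordinator calls on positive answers. No visit or procedure is added.
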